1. **30-day follow-up:** should be performed for all recruited patients. Each patient will be followed-up for 30 days starting on the day of surgery (day 0).
2. **One-year follow-up:** due to the nature of the study, aiming to assess bile duct injury and unsuspected gallbladder cancers, we aim to collect one-year follow-up data on all recruited patients. Each patient will be followed-up for one year starting on the day of surgery (day 0). Patients are excluded from one-year follow-up if they had died within 30 days of index surgery, as there would be no additional data to collect from these patients since the 30-day follow-up that had already been completed previously. Additional collaborators can be recruited to aid one-year follow-up data collection once the follow-up period begins (31st Jul 2024).

Local arrangements for successful 30-day and one-year follow-up may include: reviewing patient notes, reviewing patient status in outpatient clinics or via telephone interview at 30 days (if this is normal practice) and checking for readmission through handover lists. Follow-up should be performed in line with current routine practices of each hospital. No additional telephone, in-person or questionnaire-based follow-up is required. Source data may be acquired from hospital in-patient notes, clinical electronic systems, or outpatient letters.

Key to successful 1-year follow-up:

1. *Ensure you keep a list of all patient ID and corresponding RedCap ID in a safe, secure computer to allow follow-up of these patients. This will be in the form of an encrypted spreadsheet held securely on the local hospital computer network by a member of the data collection team (a hospital lead, supervising consultant/attending, or audit officer).*
2. *Where it is anticipated that a hospital lead will rotate to another hospital, then the supervising consultant should facilitate the secure storage of patient ID and corresponding RedCap ID.*
3. *Ensure the audit office / local governing bodies are clear this will be a follow-up study.*
4. *In high-volume centres where achieving high data completeness may be burdensome, involvement additional team members to provide support can be permitted.*

Table 1: Data collection periods

Dates	Description
00:00 31 st July – 23:59 13 th Aug 2023	Start of data collection period 1 (+ 30-day follow-up: ends 12 th Sep 2023) (+ one-year follow-up: ends 13 th Aug 2024)

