The secondary endpoints include:

- Rates of achieving a critical view of safety.
- Rates of different bailout procedures initiated when safe cholecystectomy is compromised.
- 30-day and one-year rates of textbook outcomes [2] for cholecystectomy, which covers: postoperative complications (Clavien-Dindo classification), intraoperative complications (including bile duct and vascular injuries), length of stay, readmission, mortality, and postoperative imaging or intervention.
- Unsuspected gallbladder cancer rates and their 30-day and one-year outcome rates, which includes: (1) complication rates (Clavien-Dindo classification); (2) time-to-recurrence rates (time from surgery to recurrence); and (2) revisional surgery rates (liver resection, bile duct resection and/or lymph node dissection).
- A description of the global variation in the availability of cholecystectomy services, training and sustainable practice.

Control of Bias and Confounding

Data will be collected on audit standards and confounding factors for risk-adjusted analyses. These include age, sex, body mass index, American Society of Anaesthesiologists (ASA) grade, and relevant comorbidities. Variables including operative urgency, operative contamination, and operative approach will also be collected. Without appropriately adjusting for risk factors, it is likely that any findings would be biased and unable to be appropriately analysed on an international scale. A full list of required data fields is available in **Appendix B**, and on the REDCap database.

Data Analysis & Sample Size

Variation across different international health settings will be tested using the human development index (HDI) countries [17] a composite statistic of life expectancy, education and income indices published by the United Nations. Initially, data will be reported using descriptive analyses. Comparisons between groups will be undertaken using appropriate parametric and non-parametric analyses. Multilevel logistic regression multivariate models will be constructed to account for case mix, with population stratification by hospital and country as random effects.

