8. Operation performed	Standard total cholecystectomy Total cholecystectomy by the fundus-first (top down) approach Subtotal cholecystectomy (reconstituting / fenestrated) Not performed (diagnostic laparoscopy / cholecystostomy) Definitions of subtotal cholecystectomy: 
 Fenestrated: does not occlude the gallbladder but may suture the cystic duct internally Reconstituting: closes off the lower end of the gallbladder, creating a remnant gallbladder
9. Abdominal drain insertion	Yes / No
10. Anatomical Biliary variant	Yes / No
11. Intraoperative CBD Assessment	Intraoperative cholangiogram (IOC) / Incisionless fluorescent cholangiography/ Laparoscopic ultrasound / Intraoperative ERCP If yes to any of the above: 
 Decision: Selective / Routine. If selective, state Indication: Raised liver function test / Concern of a bile duct injury / pre-operative imaging suggestive of CBD stone Findings: Stone / No stone. If stone, tick all that apply for management: Flushing with saline and smooth muscle relaxant / Fogarty catheter trawl / Basket retrieval / Choledochoscope / No intraoperative treatment attempted
12. Common Bile Duct exploration	Yes (Trancystic / Choledochotomy) / No If Choledochotomy then select closure: Primary closure / T-tube
13. Operative contamination	Clean (Gastrointestinal (GI) and genitourinary (GU) tract not entered) Clean-Contaminated (GI or GU tracts entered but no gross contamination) Contaminated (GI or GU tracts entered with gross spillage or major break in sterile technique) Dirty (There is already contamination prior to operation, e.g., faeces or bile).
14. Intraoperative complications - excluding bile duct injury (BDI) (Select all that apply)	Bile spilt / Stones Spilt / Bleeding / Major vascular injury / Bowel injury
15. Were reusable gowns used in this procedure?	Yes (All scrubbed staff/ some scrubbed staff) / No
16. Were reusable drapes used in this procedure?	Yes / No
30-day Outcomes	Required data (definition / comment)
1. Highest 30-day Clavien-Dindo (CD) Grade	0 / I / II / IIIa / IIIb / IVa / IVb / V (Appendix D for definitions) If CD IIIa: Radiological drainage (yes / No) If CD IIIb: Re-laparoscopy (yes / No) If CD V (death): please indicate time from index cholecystectomy to death: number of days (whole number, 0 = same day)

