2. Unplanned critical care admission - where critical care admission was not part of pre-operative plan	Yes / No If yes, please indicate length of stay in critical care: number of days (whole number)
3. Unplanned Re-imaging - where imaging in post-operative period (e.g.,	Yes / No If yes then tick all that apply: USS / CT / MRI / ERCP

CT, MRCP) was not part of pre-operative plan
	

4. 30-day postoperative complications (Select all that apply)
	
Surgical site infection (CD Grade* 0 / I / II / IIIa / IIIb / IVa / IVb / V) Postoperative pulmonary complications (CD Grade* 0 / I / II / IIIa / IIIb / IVa / IVb / V) Bile leak (CD Grade* 0 / I / II / IIIa / IIIb / IVa / IVb / V) Bleeding (CD Grade* 0 / I / II / IIIa / IIIb / IVa / IVb / V) Intra-abdominal collection (CD Grade* 0 / I / II / IIIa / IIIb / IVa / IVb / V) Acute pancreatitis (CD Grade* 0 / I / II / IIIa / IIIb / IVa / IVb / V) *For all of the above, please indicate the Clavien-Dindo grade associated with that complication

5. Length of stay
	
Whole number of days (Where discharge < 23 hours, enter 0. If the patient has not been discharged prior to the end of 30-day follow-up, enter '31')

6. Unplanned readmission within 30 days
	
Yes (Length of stay) / No

Bile Duct Injury (BDI) data fields
	
Required data (definition / comment)

1. BDI identified within 30-days of index cholecystectomy
	
Yes / No If yes: please fill in the rest of the data points below. If No: Was BDI identified within one-year of index cholecystectomy: Yes / No (if yes, then please fill in the rest of the data points below)

2. Presentation of BDI
	
Intraoperatively / Controlled bile leak from surgically placed abdominal drain / Abdominal pain due to uncontrolled bile leak / Obstructive jaundice or cholangitis / Intra-abdominal abscess or biloma

3. Days from index cholecystectomy to diagnosis
	
Number of days (0 = intraoperatively)

4. Bile duct injury grade
	
A / B / C / D / E1 / E2 / E3 / E4 / E5 (Strasberg Injury Grade: Appendix D for definition)

5. Concomitant vascular injury
	
Yes (Right hepatic artery / Common hepatic artery / Main portal vein / Right portal vein) / No

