
6. Imaging modality to investigate and confirm BDI
	
On-table cholangiography (OTC) / USS / MRCP / CT / ERCP / Percutaneous transhepatic cholangiography (PTC) / Nuclear medicine scan (e.g. Functional liver scan) / Tubogram / None

7. Discussion with a specialist HPB centre
	
Yes / No / Not required (Injury occurred at specialist HPB centre) If yes:
 
 Transferred to specialist HPB centre: Yes / No Time from injury to referral: number of days (whole number)

8. Management of Bile duct injury (Select all that apply)
	
Non-surgery (ERCP only / ERCP and stent / PTC) / Surgery (washout only / repair) If any of the above:
 
 Time after index cholecystectomy: number of days (Whole number, day of index cholecystectomy = day 0) 
If surgical repair:
 
 Specialty of surgeon performing Bile duct injury repair: HPB surgeon / UGI surgeon / General surgeon Method of repair: Roux-en-Y Hepaticojejunostomy / CBD repair without T-tube / CBD repair with T-tube / CBD end to end anastomosis / Hepaticoduodenostomy Vascular repair: Yes / No One-year complications: Stricture formation / Cholangitis / anastomotic leakage / intra-abdominal abscess or biloma / re-repair. If yes to any, time from repair to complication: number of days (Whole number, day of repair = day 0)

	Stricture definition: defined as a clinically relevant stricture leading to either jaundice, significant alterations of the liver function tests, cirrhosis or reoccurring cholangitis requiring radiological/surgical intervention or a liver failure related death
Histology data fields	Required data (definition / comment)
1. Postoperative histology	
Not sent for examination / Sent for examination
 
If sent for examination, please complete:
 
 • Indication: Routine / Selective • Time from index cholecystectomy to histology result: Number of days (whole number) • Result: Benign / Malignant 
If Malignant, please complete the rest of the data points below

2. Staging investigations after index cholecystectomy (select all that apply)	
CT thorax abdomen pelvis / MRI liver / PET-CT / Staging laparoscopy
 
For any of the above, please indicate time from histology result to staging investigation: number of days (whole number)

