3. TNM grade (AJCC 8th edition) (Appendix D for definition)	
T category: Tis / T1a (lamina propria) / T1b (muscularis) / T2a (peritoneal side) / T2b (hepatic side) / T3 / T4
 
N category: N0 / N1 (1-3 nodes) / N2 (>3 nodes)
 
M category: M0 / M1

4. Discussed at MDT	Yes / No
5. Adjuvant treatment	No / Chemotherapy / Radiotherapy
6. Revisional surgery completed	
Yes / No (not required) / No (unresectable tumour)
 
 • If yes, type of surgery (select all that apply): Liver resection (liver bed / one segment / two segments/ ≥ 3 segments) / bile duct resection / lymph node dissection • If yes, time from histology result to revisional surgery: Number of days (whole number)
7. Pathology results if revisional surgery	
Resection margin status: R0 / R1 / R2
 
Lymphovascular invasion: Yes / No
 
Perineural invasion: Yes / No
 
Resection margin definition: R0 = microscopically negative for residual tumor; R1 = microscopically margins still demonstrate the presence of tumor; R2 = macroscopically-visible disease remains post-surgery.

8. Recurrence on imaging at one year	
Yes / No
 
If yes, time from surgery to recurrence: number of days (whole number)

One-year Outcomes	Required data (definition / comment)
1. Highest one-year Clavien-Dindo (CD) Grade	
0 / I / II / IIIa / IIIb / IVa / IVb / V
 
If CD IIIa: Radiological drainage (yes / No)
 
If CD IV: Re-laparoscopy (yes / No)
 
If CD V (death): please indicate time from index cholecystectomy to death: number of days (whole number)

2. Readmissions	Total number of readmissions

3. One-year complications
(Select all that apply)

Surgical site infection (CD Grade* 0 / I / II / IIIa / IIIb / IVa / IVb / V)

Postoperative pulmonary complications (CD Grade* 0 / I / II / IIIa / IIIb / IVa / IVb / V)

Bile leak (CD Grade* 0 / I / II / IIIa / IIIb / IVa / IVb / V)

Biliary stricture (CD Grade* 0 / I / II / IIIa / IIIb / IVa / IVb / V)

Bleeding (CD Grade* 0 / I / II / IIIa / IIIb / IVa / IVb / V)

Intra-abdominal collection (CD Grade* 0 / I / II / IIIa / IIIb / IVa / IVb / V)

Acute pancreatitis (CD Grade* 0 / I / II / IIIa / IIIb / IVa / IVb / V)

*For all of the above, please indicate the Clavien-Dindo grade associated with that complication

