APPENDIX C: SITE SURVEY

Hospital-level services	
What is your hospital type?	Tertiary / District (Rural) / District (Non-rural)
How is your hospital funded?	Public / Private / Mixed
Total number of inpatient beds	(Number)
Do you have Level 2 (HDU) or Level 3 (ITU) facilities?	Yes (Number of beds) / No
Do you have a specialised HPB team at your centre	Yes / No If yes: (i) Are there on-call services from them: Every day 24 hour / Everyday, daytime 0800 - 1700 / Weekdays, 24 hour / Weekdays, daytime 0800 - 1700 (ii) Do they have a dedicated pathway for management of bile duct injury: Yes / No If no , are there on-call surgeons specialised in HPB: Within the same city / In other city / In the region / None
Do you have access to minimally invasive surgical equipment?	Yes (Laparoscopic / Robotic) / No If yes , do you routinely take intraoperative images? Yes (Video / Photo) / No
Cholecystectomy services	
What is the approximate total number of cholecystectomies performed each year?	(Number)
What is the number of consultants/ attending surgeons who perform cholecystectomies each year?	(Number)
Which specialist consultants/ attending surgeons perform cholecystectomies each year? (select all that apply)	General / Upper GI / HPB / Colorectal / Breast / Other
What type of services for cholecystectomy services do you provide? (select all that apply)	Elective / Emergency If emergency: 
 What is the approximate total number performed each year? (Number) Do you have dedicated theatres for these services? Yes (Everyday / Once a week / Once every 2 week / More than once every 2 weeks) / No
Where does cholecystectomy get performed on your site? (select all that apply)	Day unit / Elective theatre / Emergency theatre
Have you got access to intraoperative cholangiogram?	Yes - routinely / Yes - selectively / No if yes - selectively or no: What is the supply for these? Good supply / Limited supply / None
Number of consultants / attendings who perform laparoscopic cholecystectomy	(Number)
Do you routinely follow-up after cholecystostomy?	Yes - routinely / Yes - selectively / No

Diagnostic / treatment around gallbladders	
Types of diagnostic imaging available (select all that apply)	Ultrasound (On-site / Off-site) / Computer Tomography (On-site / Off-site) / MRCP (On-site / Off-site) / EUS (On-site / Off-site) / HIDA (On-site / Off-site)

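### Follow-up is passive and the post-operative outcome fields cannot separate no event from not ascertained, so readmission and bile duct injury comparisons across HDI groups may be biased

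*Protocol*

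**What the plan says.** Under Follow-up Period, the protocol sets follow-up for recruited patients at 30 days and one year, omitting the one-year contact only for those who died within 30 days. On method it says "Follow-up should be performed in line with current routine practices of each hospital" and "No additional telephone, in-person or questionnaire-based follow-up is required". Sources are the hospital's own notes, electronic systems and letters.

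The outcome fields in Appendices A and B are these:

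- Unplanned 30-day readmission is yes or no.
- BDI within 30 days is yes or no. If no, the next question is "Was BDI identified within one-year of index cholecystectomy", again yes or no.
- "Recurrence on imaging at one year" is yes or no, with a day recorded only if yes.
- Highest Clavien-Dindo grade starts at 0. Individual complications are tick lists.

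None of these fields offers a not-known answer. No day of last contact is recorded for any patient.

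Two completeness rules apply. Study Setting excludes a centre with more than 10% missing data from the analysis and from authorship. The Authorship section asks for more than 95% of data points per record.

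The below-10% readmission rate is one of the post-operative audit standards, and compliance with the audit standards is the primary endpoint. The section on data analysis and sample size tests variation across health settings by HDI.

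**The concern.** Under passive follow-up, a readmission or injury treated at another hospital, or in a patient who never returns, may leave no trace in the index hospital's records. The form then gives the collaborator a yes, a no or a blank. A blank counts against the centre under both completeness rules; an unsupported no does not. The likely result is that unascertained outcomes enter the data as no event.

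If the share of events found were the same everywhere, rates would be too low but relative comparisons would largely survive. The study, however, compares settings by HDI, and the quality of routine follow-up may plausibly vary along that axis. A setting with weaker follow-up would then look better on readmission and BDI for that reason alone. Case-mix adjustment cannot correct this, because the form never records who was ascertained.

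**Working it through.** No figure stated in the protocol depends on this point, so there is none to reproduce. The check has two parts: whether anything else in the plan supplies the missing distinction, and how large the bias could be.

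**Does anything else supply it?**

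- *Self-reported methods (Data Validation).* Hospitals report how outcomes were determined, but only for 30 days. One year is not mentioned, and no matching field appears in Appendices A to C.
- *Independent validation.* Validators cover two outcome measures and work from records at their own centre. They would not see events treated elsewhere.
- *Site survey (Appendix C).* The only question on routine follow-up reads "Do you routinely follow-up after cholecystostomy". That is a different procedure, so as worded the answer does not describe follow-up after cholecystectomy.
- *Clavien-Dindo grade 0.* This partly serves as a none answer, but it does not separate none from not known.

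**How large could the bias be?** Recorded rate = true rate × share of events found. The true readmission rates and all shares found are assumptions; the documents give none.

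*Readmission, standard below 10%.* A centre or group appears to meet the standard once the share found is below 0.10 / true rate:

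| True rate | Share found below which it appears to pass |
|---|---|
| 11% | 0.10 / 0.11 = 90.9% |
| 12% | 0.10 / 0.12 = 83.3% |
| 15% | 0.10 / 0.15 = 66.7% |

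With a true 12% in two groups and 95% against 60% found, the recorded rates are 0.12 × 0.95 = 11.4% (fails) and 0.12 × 0.60 = 7.2% (passes). The odds ratio is (0.072/0.928) / (0.114/0.886) = 0.60, with no true difference. With 80% found, the rate is 0.12 × 0.80 = 9.6%, which also passes.

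*BDI.* The audit standards quote 0.4% (elective) and 0.8% (emergency). Take the midpoint, 0.6%, as the true rate in both groups. Split the anticipated 15,000 patients into two groups of 7,500, with 95% of events found in the first. The chance of a two-sided p < 0.05 is about Φ(z − 1.96), where z = (p1 − p2) / √[(p1(1 − p1) + p2(1 − p2)) / 7500].

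| Found in second group | Recorded rates | Chance of a spurious difference | Range for true rate 0.4% to 0.8% |
|---|---|---|---|
| 80% | 0.57% v 0.48% | 12% | 9% to 14% |
| 60% | 0.57% v 0.36% | 47% | 34% to 59% |
| 40% | 0.57% v 0.24% | 89% | 74% to 96% |

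For the middle row, z = 0.0021 / 0.00111 = 1.89, and Φ(1.89 − 1.96) is about 0.47. The calculation ignores clustering by hospital and country, so the chances are rough.

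**The case against.** The strongest reply is that passive follow-up is deliberate. Using only routine data lets centres register the study as audit, so the follow-up rule is not itself an error. That stands, and the fix below leaves it alone. It is also fair that no text tells sites to enter no for a patient not seen; a field can be left blank. That outcomes will be entered as no is an inference from the response options and the completeness rules.

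The effect on the primary endpoint is limited too. Most audit standards (imaging access, critical view, drains, antibiotics and others) do not depend on follow-up; readmission and BDI do. The protocol also says attainment of some standards will not be treated as a definitive measure of quality. Denominators and censoring rules may properly sit in a SAP, but a SAP cannot supply a field that was not collected.

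Four stronger readings are tempting and are not supported:

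- *Histology has the same fault.* It does not. The field reads "Not sent for examination / Sent for examination", so an unexamined gallbladder is distinct from a benign one, and the site survey records each hospital's histology practice.
- *Time to recurrence cannot be censored at all.* It can be censored at one year or at death, since day of death is collected. Only loss before one year is invisible.
- *The intra-operative list ("Bile spilt / Stones Spilt / Bleeding / Major vascular injury / Bowel injury") shows the same problem because it has no none option.* Those events are seen in theatre and do not depend on follow-up.
- *The form never allows an unknown answer.* Pre-operative imaging does; the gap is in the post-operative outcome fields.

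**Conclusion.** The point holds for readmission, BDI at 30 days and one year, recurrence and, less sharply, the Clavien-Dindo and complication fields. As designed, the data cannot separate no event from not ascertained, and the existing safeguards close the gap only in part.

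The size is unknown, because it depends on shares of events found that the documents do not give. Under the assumptions shown, a true 12% readmission rate passes the standard once fewer than about 83% of readmissions are found. Finding 95% against 60% of BDIs gives roughly an even chance of a spurious difference.

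Bias in the HDI comparison is conditional on ascertainment differing by HDI group. That is plausible but not stated anywhere. A reader might infer that the ranking of settings would be reversed; the illustration does not show this, because it starts from equal true rates and shows only an apparent difference where none exists. For time to recurrence, the loss is confined to patients lost before one year.

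**What to change.** 1. Add a not known / not ascertained answer to readmission, BDI at 30 days and at one year, recurrence, and the Clavien-Dindo and complication fields at both timepoints.
2. State that this answer counts as a completed data point under the 10% exclusion rule and the 95% authorship rule, so that an honest answer carries no penalty.
3. Record days from surgery to last known status, and its source, at both timepoints.
4. Report readmission and BDI among patients with known status, with best-case and worst-case bounds by HDI group. Censor time to recurrence at last known status.
5. Reword the site-survey question so that it asks about follow-up after cholecystectomy.

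The cost is a few response options and one day-and-source item per timepoint, with no new patient contact. Stated follow-up completeness will look lower, because the gaps become visible. The bounds for BDI may be wide: the worst case exceeds the best case by the whole unknown share, so an unknown share of only 0.8% already equals the emergency benchmark. That width would be an honest statement of what the data can support.
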